Due to the indolent nature of the lymphoma, most patients are diagnosed with advanced disease, including bone marrow involvement, in the absence of B symptoms.² The disease is staged according to the criteria of the Lugano classification (*Appendix C – Lugano modification*).²¹ Currently, the treatment of patients is still guided by staging. Radiotherapy with curative intent is proposed for patients with stage I or II disease. For patients with contraindications for radiotherapy, clinical observation or treatment with rituximab, alone or in combination with chemotherapy, may be considered.^{22, 23} For patients with advanced disease, no curative therapy is established, and treatment should only be initiated in case of symptomatic disease according to the GELF criteria (*Appendix D – GELF criteria*).

The choice of treatment in patients with advanced disease varies according to patient's performance status, age, comorbidities and purpose of therapy, but usually comprises of rituximab in combination with chemotherapy such as CHOP, CVP, FM, bendamustine, or novel agents such as lenalidomide for patients enrolled in clinical trials.^{24–26}

Response evaluation should be performed midterm and after completion of chemotherapy. Patients who achieve a complete or partial remission can be treated with rituximab maintenance for 2 years as this results in an improvement of PFS (59% versus 43% after 6 years, $p < 0.0001$).²⁷ On the other hand, patients with an inadequate response should be evaluated for early salvage regimens. The use

of FDG_PET-CT after completion of chemotherapy induction has been recommended for prognostic reasons since persistent PET positivity identifies a worse prognosis group.²⁸

FL follows a chronic relapsing course and a new course of treatment is indicated based on GELF criteria. Histologic documentation of progressive disease and exclusion of transformation² are highly recommended before the start of new lines of therapy.² For patients requiring a second line of treatment, the chemotherapy regimen used in first line may be employed again if relapse occurs after an interval of at least 24 months. Otherwise, a non-cross-resistant scheme should be preferred. Obinutuzumab is an option for patients with rituximab refractory disease^{22, 23, 29} as well as the PI3K inhibitor idelalisib.³⁰ Autologous transplantation is an option to be considered as consolidation in first relapse, especially in young patients with short remission.³¹

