3. ENDPOINTS

Primary Endpoints

- Rate of Progression of disease within 24 months from start of second line treatment (second POD24)

Secondary Endpoints

- Overall Survival (OS)
- Progression-free survival after second line therapy (second PFS)
- Complete response rate at 30 months (CR30) from start of second line treatment (second CR30)

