5. STUDY PROCEDURES

5.1 Patient enrollment and registration

Patients with histologically confirmed follicular lymphoma are registered in the study at the time of the first event after first line treatment. An event is defined as refractory/relapsed disease documented by biopsy, imaging, or clinical evaluation. Registration is based on the locally established histological diagnosis, with exclusion of cases diagnosed on fine needle aspiration cytology, while tru-cut core-needle biopsies are permitted in the study. Registration will be done on-line on a key restricted accessible web-database: the Investigator must complete the on-line registration form after obtaining informed consent dated and signed by the patient.

Investigators are requested to register consecutive cases diagnosed at each participating Institution (all patients satisfying Inclusion criteria without any further selection). Inclusion criteria will be checked at the Trial Office. A patient number (Patient ID) will be assigned strictly sequentially in ascending order as patient's eligibility is verified. In case a patient's eligibility is not confirmed by the Trial office and the patient is withdrawn from the study, the patient number will not be reused.

The assigned number will be used as the identification code for the subject. A space will be provided for the Clinician to enter a local alphanumeric code to better identify the patient.

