6.4 Endpoint definition

The endpoints of interest in the present study have been adapted from the Standardize Response Criteria for Non-Hodgkin's Lymphoma and from Recommendations for Revised Response Criteria for Malignant Lymphoma (*Appendix C2_Revised Response Criteria for malignant lymphoma*). In particular:

- Second POD24 is defined as the rate of progression of disease at 24 months after the second line treatment;
- OS is measured from the date of diagnosis until death from any cause;
- Second PFS is measured from the date of study entry until the date of disease progression or death from any cause;
- Second CR30 is defined as the rate of complete remissions at 30 months from start of second line treatment.

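### Second PFS is named for second-line therapy but timed from study entry, which is the first relapse or refractory event and may precede that therapy

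*Protocol*

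**What the plan says.** Section 3 lists the secondary endpoint as "Progression-free survival after second line therapy (second PFS"). Section 6.4 sets its clock: "Second PFS is measured from the date of study entry until the date of disease progression or death from any cause".

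Section 5.1 says when study entry occurs. Patients are "registered in the study at the time of the first event after first line treatment", and "An event is defined as refractory/relapsed disease documented by biopsy, imaging, or clinical evaluation". The trigger is disease status, not the start of treatment. The inclusion criteria in section 4.1 do not require that second-line treatment has started or is planned.

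The neighbouring endpoints use another origin. Section 3 gives the primary endpoint as "Rate of Progression of disease within 24 months from start of second line treatment (second POD24"), and section 6.4 times CR30 from the start of second-line treatment. Section 6.4 words the primary endpoint less exactly: "Second POD24 is defined as the rate of progression of disease at 24 months after the second line treatment".

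Section 6.1 bases the sample size on PFS counted from relapse or refractory disease. That agrees with the study-entry clock but not with the endpoint's name. Appendix E collects start and end dates for each treatment line, and the time to each treatment.

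**The concern.** The endpoint's name and its definition describe different quantities. The first study objective concerns prognosis after second-line therapy, yet the second PFS clock starts at an event that may come before that therapy. The Introduction makes a gap plausible: "FL follows a chronic relapsing course and a new course of treatment is indicated based on GELF criteria". In an observational study with no rule on when treatment must begin, some relapses may be watched for a time.

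Following section 6.4 literally has four effects:

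- Event-free time before treatment is credited to second-line PFS.
- A progression during observation, including one that prompts second-line treatment, can count as a second PFS event although it cannot be a failure of that treatment.
- Patients who never start second line contribute to second PFS but have no time zero for POD24 or CR30.
- Hazard ratios from the Cox models in section 6.2 would mix factors that drive deferral with factors that drive treatment failure.

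The 24-month Kaplan-Meier estimate of second PFS would also be on a different clock from the primary endpoint, beside which it will naturally be read.

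**Working it through.** **The text.** The contradiction needs no arithmetic. Section 3 names the endpoint for second-line therapy, section 6.4 starts it at study entry, and section 5.1 puts study entry at the first event after first line. No section states that entry and second-line start are the same date.

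**The Protocol's own figure.** Section 6.1 gives a Weibull with λ = 0.008 (months) and shape p = 0.97, 500 patients and 145 events. It does not say which parameterisation is meant, so both were used:

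- Form 1: S(t) = exp(−λt^p)
- Form 2: S(t) = exp(−(λt)^p)

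Expected events are 500 × the mean of 1 − S(u) over uniform accrual. Form 1 gives 144.3 with 24 months' accrual and 60 months in total. Form 2 gives 145.3 with 36 months' accrual and 60 in total. With 24 months' accrual and only the two-year minimum follow-up, the results are 113.4 and 128.6. So 145 is attainable, but it cannot be confirmed from the stated inputs because accrual and follow-up for the 500-patient plan are not fixed. It is not shown to be wrong, and this point does not depend on it.

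**Effect of the time origin.** Two assumptions are needed. The Weibull is applied from second-line start, although section 6.1 words it from relapse. Every patient has the same event-free delay of d months between entry and treatment, and d is not in the documents. Then:

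- progression or death by 24 months from treatment start = 1 − S(24)
- the same patients, by 24 months from entry = 1 − S(24 − d)

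Form 1: 24^0.97 ≈ 21.82, × 0.008 ≈ 0.1745, so S(24) = 0.8398. Form 2: (0.192)^0.97 ≈ 0.2017, so S(24) = 0.8173.

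| Delay d (months) | Form 1 | Form 2 | Fall (points) |
|---|---|---|---|
| 0 | 16.0% | 18.3% | – |
| 1 | 15.4% | 17.6% | 0.6–0.7 |
| 3 | 14.2% | 16.2% | 1.8–2.0 |
| 6 | 12.4% | 14.2% | 3.7–4.1 |
| 12 | 8.5% | 9.8% | 7.5–8.5 |

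**When the direction reverses.** Suppose a fraction q progresses during the delay and this counts as an event. PFS at 24 months from entry becomes (1 − q) × S(24 − d). It drops below S(24) once q exceeds 1 − S(24)/S(24 − d):

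- d = 12: 1 − 0.8398/0.9148 = 8.2% (form 1); 1 − 0.8173/0.9021 = 9.4% (form 2)
- d = 1: 1 − 0.8398/0.8458 = 0.7% (form 1); 1 − 0.8173/0.8240 = 0.8% (form 2)

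The documents give neither q nor d, so the sign of the distortion is unknown as well as its size.

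**The case against.** The strongest reply is that the entry-based clock may be intended and only the label is wrong. PFS from first relapse is a legitimate quantity, it is defined for every registered patient, and section 6.1 sizes the study on it. This stands as far as it goes: the document does not show which of the two was meant, and renaming would also remove the contradiction. It does not rescue the text as written, because section 3 and the first objective promise an outcome after second-line therapy.

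Second, the endpoint is secondary, and treatment dates are collected, so the right analysis remains recoverable. If nearly all patients start promptly, the effect is well under one percentage point at a 1-month delay. This stands and bears on severity.

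A reader might also infer four stronger points that the documents do not support:

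- **Long deferral is built in.** The GELF sentence is Introduction background, is not worded as an exclusive condition, and gives no duration. Section 4.1 also admits refractory and transformed disease. Deferral is possible but not quantified.
- **The distortion is large.** Assume an exponential with a 36-month median and non-deferring patients starting at 1 month. Then 24-month PFS moves from 63% to 67% if 20% defer for 12 months, and to 75% if 30% defer for 24 months. Neither that median nor those fractions appear in the Protocol. Under the section 6.1 Weibull, form 1, the same scenarios give 0.8 × 0.8458 + 0.2 × 0.9148 = 86.0% and 0.7 × 0.8458 + 0.3 = 89.2%, against 84.0%. Form 2 gives 84.0% and 87.7%, against 81.7%. The shifts are about 2 and 5–6 points.
- **A common origin would make second PFS agree with POD24.** It would not do so fully. Section 6.4 counts death in PFS, whereas POD24 is worded as progression only.
- **Endpoints with different origins are wrong in themselves.** They are not. The fault is the mismatch between this endpoint's name and its clock.

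**Conclusion.** The point holds. Second PFS carries the name of an outcome after second-line therapy but is timed from an event that may precede it. This is a definition fixed in section 6.4, not a detail left to a later analysis plan.

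Under the assumptions above (section 6.1 Weibull from treatment start, a common event-free delay of 1 to 12 months), the entry-based clock lowers 24-month progression or death by about 0.6 to 8.5 percentage points from 16.0–18.3%. The direction can reverse if pre-treatment progression is counted. These figures show sensitivity to the clock; they do not estimate the bias in this study.

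The primary endpoint does not use study entry under either of its wordings, though its own origin is stated inconsistently (from the start of second-line treatment in section 3, after that treatment in section 6.4). Because the endpoint is secondary and the dates are collected, this should be fixed but does not threaten the study as a whole.

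**What to change.** - **Section 6.4:** time second PFS from the start of second-line treatment to progression or death, in patients who start it, using the dates already in Appendix E.
- **All registered patients:** report time from registration to second-line start, so that deferral and non-treatment are visible.
- **If the entry-based quantity is kept** because section 6.1 sizes on it, label it PFS from first relapse/study entry and report it beside the treatment-start version.
- **Sections 3, 6.1 and 6.4:** use one stated origin per endpoint. This includes saying whether POD24 runs from the start or the end of second-line treatment, and which origin the 145-event projection uses.

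No new data are needed, but the cost is somewhat more than wording. Restricting to treated patients and moving the clock changes the set behind the 500-patient, 145-event projection, which should be restated. Section 6.3 guarantees two years from enrollment, so a patient who defers for 12 months may have only 24 − 12 = 12 months from the new origin and would be censored early. POD24 timed from treatment start already faces that limit.

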7. WITHDRAWAL OF PATIENTS

Patients may withdraw consent and discontinue participation in the study at any time, with no effect on their medical care or access to treatment.

All information already collected as part of the study will be retained for analysis; however, no further efforts will be made to obtain or record additional information regarding the patient. If the last assessment was more than three months prior to withdrawal from study and patient status has not been documented, if possible a final assessment of treatment status should be reported.

Moreover, patients can be withdrawn in case of:

- Lack of eligibility criteria;
- Histological revision reveals a diagnosis other than those in the inclusion criteria;
- Missing data; warnings will be periodically sent to the Investigators. In case of persistent missing data, the patient can be excluded from the study.

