4.1 Subject selection

Inclusion criteria

- Patients with initial diagnosis of follicular lymphoma, refractory/relapsed/transformed after first line therapy;
- All stages at the time of relapse;
- Histological grade 1-3a at the time of initial diagnosis;
- Age over 18 years;
- Availability of clinical data, including baseline information, comorbidities, data on disease localization, laboratory parameters at staging, features of treatment adopted and assurance of follow-up updating as requested - Data collection list (*Appendix E_Data collection list*)
- Diagnostic material available for review;
- Written informed consent.

Exclusion Criteria

- Age < 18 years

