6. STATISTICAL CONSIDERATIONS

6.1 Sample size

Sample size calculation is based on the aim of defining the prognosis of refractory/relapsed FL after second line therapy. To evaluate number of recordable events, we hypothesize that PFS after refractory/relapse has a risk function which follows Weibull distribution with time parameter (in months) $\lambda = 0.008$ and form parameter $p = 0.97$. After 10,000 Monte Carlo simulations we calculated that with **500** prospective cases enrolled, we would observe **145** events at the end of the study. If, for

epidemiological reasons, it will be difficult to record 500 cases, we plan to enroll all cases in two years from the study start.

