6.2 Statistical analysis plan (SAP)

Descriptive variables: continuous variables will be expressed as median and inter-quartile distance, while categorical variables will be reported as absolute frequencies and percentages. Continuous variables will be compared with the use of the Mann-Whitney test (2 groups) or the Kruskal-Wallis test (three or more groups), while categorical variables will be compared through the use of Fisher's exact test or Chi-square test as appropriate.

Survival analyses: survival functions will be calculated utilizing Kaplan-Meier method and survival rate at specific time-points will be expressed with the correspondent 95% confidence interval (95CI). The effect related to potential variables with prognostic value will be estimated through Cox proportional risk regression and will be expressed as hazard ratio (HR) with 95CI. Risk proportionality will be verified through Schoenfeld partial residual analysis, both graphically and through cubic-spline smooth linear regression. The influence of residues will be evaluated through likelihood displacement as a function of the residues martingala analysis.

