6.3 Study duration

Patients will be followed for at least two years after enrollment. However, a five year follow-up period is desirable (an update is requested at least every 6 months).

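### Section 7 lets a registered, eligible patient be excluded for persistent missing data and does not say that the data already collected stay in the analysis, which can bias second POD24, PFS and OS in either direction

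*Protocol*

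**What the plan says.** Section 7 has two parts. The first concerns patients who withdraw consent, and there it says: "All information already collected as part of the study will be retained for analysis". The second is a separate list of further reasons for withdrawing a patient: failed eligibility, a histology review that gives a diagnosis outside the inclusion criteria, and missing data. For missing data, investigators receive periodic warnings, and then "In case of persistent missing data, the patient can be excluded from the study". The rule names no amount or duration of missingness, no variables and no decision-maker. It does not say whether such a patient's data are analysed.

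Four other places bear on this:

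- Section 5.1 asks sites to register consecutive cases, meaning "all patients satisfying Inclusion criteria without any further selection".
- Section 4.1 makes availability of clinical data and "assurance of follow-up updating as requested" an inclusion criterion.
- Section 6.2 plans Cox regression and states that "survival functions will be calculated utilizing Kaplan-Meier method".
- Section 6.3 says "Patients will be followed for at least two years after enrollment", calls five years desirable and asks for an update at least every six months.

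**The concern.** The first purpose in Section 2 is to define prognosis after second-line therapy, and Section 3 makes the 24-month progression rate primary. A descriptive rate of this kind is only as good as its denominator. The missing-data rule allows that denominator to be changed after registration, by discretion, when outcomes have already begun to accrue. The other two reasons in the list concern patients who should not have been in the cohort. A patient with gaps in the record is still a member of it.

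With six-monthly updates over two to five years, gaps are foreseeable. If these patients are deleted rather than censored, the follow-up they did contribute is lost, and the remaining patients are selected on completeness of the record. Enrolling more patients does not remove such a bias.

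**Working it through.** **Inputs.** From Section 6.1: N = 500, 145 expected events, and a Weibull for PFS with λ = 0.008 per month and p = 0.97. The protocol does not say which Weibull form is meant, so both are carried: A, S(t) = exp(−λt^p); B, S(t) = exp(−(λt)^p). Assumptions, because the protocol gives no figures: 10% or 20% lost by 24 months; 10% or 15% excluded; progressors two or three times as likely to be excluded. PFS at 24 months stands in for second POD24.

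**1. The plan's own figure.** 145/500 = 29%. The two-year enrolment period appears only as a fallback ("we plan to enroll all cases in two years from the study start"). With uniform accrual over 24 months plus 24 months of minimum follow-up, the inputs give 113 events (A) or 129 (B). Timings that the protocol does not state come close to 145: 48 months for every patient under A (144.8), 24 + 36 months under A (144.3), or 24 + 30 months under B (146.1). The end of study is not dated, so 145 can be neither confirmed nor refuted. Nothing below depends on it.

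**2. Implied 24-month progression.**

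- A: 24^0.97 = 21.82; × 0.008 = 0.1745; 1 − exp(−0.1745) = 16.0%.
- B: (0.008 × 24)^0.97 = 0.2017; 1 − exp(−0.2017) = 18.3%.

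95% half-width at 500 patients, 1.96 × √(P(1 − P)/500): 3.2 points (A), 3.4 points (B).

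**3. Loss unrelated to outcome.** In 200,000 simulated patients with independent exponential loss, the Kaplan-Meier 24-month estimate was taken twice: with lost patients censored, and with them deleted.

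| Form | True | Loss by 24 months | Censored | Deleted |
|---|---|---|---|---|
| A | 16.0% | 10% | 16.0% | 16.7% |
| A | 16.0% | 20% | 16.0% | 17.6% |
| B | 18.3% | 10% | 18.3% | 19.1% |
| B | 18.3% | 20% | 18.3% | 20.2% |

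As a check, the deleted estimate equals E/(1 − L). E is the probability of an event by 24 months that occurs before loss, and L is the probability of loss before both the event and 24 months. Numerical integration gives 0.1524/0.9082 = 16.8% and 0.1443/0.8161 = 17.7% for A, and 0.1738/0.9094 = 19.1% and 0.1646/0.8185 = 20.1% for B, within about 0.1 point of the simulation. The shift is upward because only patients with no event yet observed can be deleted.

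**4. Exclusion related to outcome.** Let P be the true rate, f the overall fraction excluded and r the exclusion ratio, progressors to non-progressors. Non-progressors are excluded at rate a = f/(Pr + 1 − P) and progressors at rate ar. The observed rate is P(1 − ar)/(1 − f). For A with f = 0.10 and r = 2: a = 0.10/1.1602 = 0.0862, and the observed rate is 0.1602 × (1 − 0.1724)/0.90 = 14.7%.

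| f | r | A: observed (bias) | B: observed (bias) |
|---|---|---|---|
| 10% | 2 | 14.7% (−1.3) | 16.9% (−1.4) |
| 10% | 3 | 13.8% (−2.3) | 15.8% (−2.4) |
| 15% | 2 | 14.0% (−2.0) | 16.0% (−2.2) |
| 15% | 3 | 12.4% (−3.6) | 14.4% (−3.9) |

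The opposite pattern reverses the sign. Excluding 5% of progressors and 20% of non-progressors gives 18.5% (+2.4) under A and 21.0% (+2.7) under B.

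**The case against.** The rule is permissive, follows warnings to the sites and may seldom be used. How analysis sets are defined may also be settled in a SAP that is not shown. Both points bear on severity. They do not rescue a sentence that, as written, allows eligible patients to leave the cohort at discretion.

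Four stronger readings are tempting, and the protocol does not support them.

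- **That Section 7 contradicts Section 5.1.** Section 5.1 governs whom sites register, not who is kept afterwards. The rule defeats the purpose of unselected registration but does not contradict its text.
- **That Section 7 contradicts itself, or certainly discards known events.** The retention sentence belongs to consent withdrawal. If it extends to the later list, the data are kept; if not, the two rules cover different cases. The text leaves this open.
- **That deaths would drop out as missing data.** Section 6.4 counts death as an event for PFS and OS, and Appendix E collects its date and cause. A documented death or progression is an outcome.
- **That the rule selects only on follow-up.** Missing data could also mean baseline items. Exclusion would then select on completeness of the record in another way.

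It can also be argued that Section 4.1 already makes persistent gaps an eligibility failure. This has force: deleting the missing-data reason alone would let the same exclusion return as ineligibility, so the fix has to cover Section 4.1.

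Finally, censoring is not a full remedy. If loss depends on outcome, censoring is informative too and some bias remains. Nor does it settle CR30, which is a response proportion at a fixed time.

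**Conclusion.** The point holds as a should-fix. The protocol permits undefined, discretionary exclusion of eligible patients for missing data and does not say that their data stay in the analysis. If the option is used and the data are removed, the estimates can be biased even when loss has nothing to do with outcome: upward by about 0.8 points at 10% loss and 1.6 to 1.9 points at 20%. Outcome-dependent exclusion of 10 to 15% at a ratio of 2 to 3 lowers the estimate by 1.3 to 3.9 points. In three of the four scenarios under each Weibull form the bias is smaller than the 3.2 to 3.4 point half-width, and in the fourth it is larger. It can therefore be comparable to sampling error, but it need not dominate it.

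These sizes rest on the protocol's Weibull standing in for second POD24 and on assumed loss and exclusion rates. The actual size and direction are unknown. A reader might infer a larger bias from a higher base rate, but no higher 24-month rate after second-line therapy is stated in the protocol.

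**What to change.** 1. Delete missing data from the Section 7 reasons for withdrawal. Keep ineligibility and a histology review outside the inclusion criteria.
2. State that every registered, eligible patient and all data collected on that patient remain in the analysis.
3. Estimate second POD24 and second PFS by Kaplan-Meier with censoring at the last documented disease assessment, and OS with censoring at the last date known alive. Appendix E already collects the date of last contact and the disease status at that contact.
4. State in Section 4.1 that the data-availability and follow-up criterion is judged at registration only and is not a ground for later removal.
5. Report the number of patients with incomplete follow-up and the reasons, and show completeness of follow-up beside the estimates, because censoring does not remove bias from outcome-dependent loss.

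The cost is a change of wording in two sections and a short completeness table. The periodic warnings to investigators can stay.
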